2.5.3 Handling of missing values/censoring/discontinuations

For the computation of CBR (CR, PR or SD) in case of solid tumor all confirmed responses (CR or PR) reported up to the analysis cut-off will be included. Patients with no valid radiological assessment or unconfirmed responses will be considered as non-responders. In particular, patients with CR or PR at the last radiological assessment prior to cut-off and no response at the previous assessment are by definition unconfirmed and will be considered as non-responders for the primary analysis.

Patients with unknown or missing BOR will be counted as failures (non-responders). If there is no baseline tumor assessment, all post-baseline overall lesion responses are expected to be 'Unknown'. If no valid post-baseline tumor assessments are available, the BOR must be

‘Unknown’ unless progression is reported. For the computation of CBR, these patients will be included in the FAS and will be counted as ‘non-responders’.

2.5.4 Supportive analyses

Not Applicable.

2.6 Analysis of the key secondary objective

2.6.1 Key secondary endpoint

Not Applicable

2.6.2 Statistical hypothesis, model, and method of analysis

Not Applicable

2.6.3 Handling of missing values/censoring/discontinuations

Not Applicable

2.7 Analysis of secondary objective(s)

For all efficacy parameters, data will be listed, summarized, or analyzed by tumor group.

The secondary objectives for this study are as follows:

- To assess overall response rate (ORR) by RECIST 1.1 in solid tumors and by Revised Response Criteria for Malignant Lymphoma (Cheson et al 2007) in lymphoma
- To assess TTR, DOR, TTP and PFS rate at 1 and 2 years
- To assess safety and tolerability of the study drugs

2.7.1 Secondary endpoints

The secondary endpoints of this study are as follows:

- Overall response rate (ORR): ORR is determined by investigator assessment for each tumor assessment in the study. For patients with solid tumors, the assessment criteria will be RECIST 1.1 and will include responses of CR and/or PR for ≤ 24 weeks. For hematological tumors, other appropriate criteria (see Protocol Appendix section for corresponding criteria) will be used to determine the responses. Additionally, estimates with corresponding 95%CI will also be provided for ORR by end of study.
- Time to Response(TTR) defined as the time from the date of first dose to the date of first documented response of CR or PR. All patients will be included in time to response calculation. For solid tumor patients who did not achieve a confirmed PR or CR will be censored
 - at maximum follow-up (i.e. FPFV to LPLV used for the analysis) for patients who had a PFS event (i.e. either progressed or died due to any cause)
 - at last adequate tumor assessment date otherwise.

- Time to Progression (TTP) defined as the time from the date of first dose to the date of first documented disease progression or relapse. If a patient has not had an event, time to progression is censored at the date of last adequate tumor assessment. Died subjects without documented progression will also be censored at the date of last adequate tumor assessment
- Duration of Response (DOR) defined as the time from the first documented response to the date first documented disease progression or relapse or death due to any cause. DOR applies only to patients who responded, e.g., for solid tumor, responder is defined as the patient's best overall response being CR or PR. The start date is the date of first documented response, and the end date is the date of event defined as the first documented progression/relapse or death due to any cause within 150 days of the last study drug dose date. In other words, the start date will be determined using the time the response was first determined and not using the time the response was confirmed. If a patient has not had an event, duration is censored at the date of last adequate tumor assessment.
- Progression Free Survival (PFS) defined as the time from the date of first dose to the date of first documented disease progression or relapse or death due to any cause during study medication or within 150 days from last dosing date, and is calculated as $PFS = (\text{date of progression/relapse or death} - \text{date of first study treatment} + 1)$. Disease progression noted as the reason for discontinuation of treatment will also be considered as a progression event for PFS analyses. If a patient has not had an event, progression free survival is censored at the date of last adequate tumor assessment
- Safety and tolerability based on number of incidences of AEs, SAEs, severe AEs, changes in laboratory parameters, vital signs and ECGs, drug interruption, reduction and dose intensity.

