2.2 Rationale for the study design

There is currently a lack of validated patient preselection markers for combination immunotherapy. Given robust early clinical and/or preclinical evidence supporting the potential

efficacy of combination CPB in several tumor types, a clinical trial employing a broad signal finding strategy across multiple tumor types is warranted. This is a phase II, open-label, study to determine the efficacy and safety of treatment with the combination of PDR001+LAG525 in patients with a diagnosis of select solid tumors or lymphoma, that are hypothesized to respond to combination CPB therapy based on existing clinical and/or preclinical data.

There are patterns of disease response unique to CPB therapy including delayed responses and apparent disease progression prior to response (pseudoprogression). In melanoma patients treated with CTLA-4 blockade, the median time to response in patients who achieved an ultimate complete response was 30 months (Prieto PA et al 2012). In a study of the anti-PD-1 mAb pembrolizumab, 10% of patients had apparent disease progression before achieving clinical benefit in the form of either stable disease or partial response (Hodi SF et al 2014). Consequently, there are limitations to using time-dependent overall response rate as the primary endpoint in a study evaluating combination CPB therapy, since immune-mediated anti-tumor effects may manifest clinically as long standing stable disease or delayed responses. Therefore, the primary endpoint for this study will be the clinical benefit rate (CBR) at 24 weeks of treatment, with a secondary endpoint of overall response.

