10.5 Secondary objectives

10.5.1 Secondary efficacy objectives

Tumor response will be determined per local investigators' assessment, according both RECIST 1.1 and the Revised Response Criteria for Malignant Lymphoma, (Cheson et al 2007). Response related efficacy assessments will be defined and analyzed based on both RECIST 1.1 and the Revised Response Criteria for Malignant Lymphoma, (Cheson et al 2007).

For all efficacy parameters, data will be listed, summarized, or analyzed by tumor group.

The secondary objectives of the study:

- To assess Overall Response (OR) of Partial Response (PR) or Complete Response (CR) based on local investigator assessment. For patients with solid tumors the assessment criteria will be RECIST 1.1 and will include responses of CR and/or PR. For lymphoma the Revised Response Criteria for Malignant Lymphoma (Cheson et al 2007) criteria will apply. Response criteria are included in the appendices. The overall response rate (ORR, PR plus CR) and its 95% exact confidence interval will be provided for each patient group. In the event where sample size in each patient group is small (<10), only ORR summary for entire study cohort will be presented
- To assess the following, based on local investigator assessment per RECIST 1.1 for solid tumors, or the Revised Response Criteria for Malignant Lymphoma (Cheson et al 2007) for lymphoma:
 - Time to Progression (TTP)
 - Time to Response (TTR)
 - Progression Free Survival (PFS)
 - Duration of Response (DOR)
- To assess safety and tolerability.

Time to progression (TTP) is defined as the time from the date of first dose to the date of first documented disease progression or relapse. Time to response (TTR) is defined as the time from the date of first dose to the date of first documented response of CR or PR. The secondary efficacy variable progression free survival (PFS) is defined as the time from the date of first dose to the date of first documented disease progression or relapse or death due to any cause during study medication or within 150 days from last dosing date.

PFS, TTP and TTR will be summarized and graphed using the Kaplan-Meier product-limit method for each patient group. Patients who drop-out without progression will be censored at

the time of last adequate assessment. The estimates of the 25th, median, 75th percentiles of the PFS and their 95% confidence intervals will be provided, if applicable.

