14.1.17 Best overall response

The best overall response is the best response recorded from the start of the treatment until disease progression/recurrence (taking as reference for PD the smallest measurements recorded since the treatment started). In general, the patient's best response assignment will depend on the achievement of both measurement and confirmation criteria.

The best overall response will usually be determined from response assessments undertaken while on treatment. However, if any assessments occur after treatment withdrawal the protocol should specifically describe if these will be included in the determination of best overall response and/or whether these additional assessments will be required for sensitivity or supportive analyses. As a default, any assessments taken more than 30 days after the last dose of study treatment will not be included in the best overall response derivation. If any alternative cancer therapy is taken while on study any subsequent assessments would ordinarily be excluded from the best overall response determination. If response assessments taken after withdrawal from study treatment and/or alternative therapy are to be included in the main endpoint determination, then this should be described and justified in the protocol.

Where a study requires confirmation of response (PR or CR), changes in tumor measurements must be confirmed by repeat assessments that should be performed not less than 4 weeks after the criteria for response are first met.

Longer intervals may also be appropriate. However, this must be clearly stated in the protocol. The main goal of confirmation of objective response is to avoid overestimating the response rate observed. In cases where confirmation of response is not feasible, it should be made clear when reporting the outcome of such studies that the responses are not confirmed.

- For non-randomized trials where response is the primary endpoint, confirmation is needed.
- For trials intended to support accelerated approval, confirmation is needed

- For all other trials, confirmation of response may be considered optional.

The best overall response for each patient is determined from the sequence of overall (lesion) responses according to the following rules:

- CR = at least two determinations of CR at least 4 weeks apart before progression where confirmation required or one determination of CR prior to progression where confirmation not required

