2.7.2 Statistical hypothesis, model, and method of analysis

The overall response rate (ORR, PR plus CR) and its two sided exact binomial 95% confidence interval will be provided for each patient group. The number and percentage of patients for different categories of overall response (e.g., for solid tumor - CR, PR, SD, PD, and NE) will be presented. These analyses will be performed with all solid tumor types combined and separately for each hematological tumor type. For tumor types that have ten (10) or more patients (within the solid tumors), separate summaries will be performed by the tumor type. In the event that there are fewer than 4 patients for a hematological tumor type, only listing will be provided for that tumor type. Additionally, the above analysis will also be repeated for overall response rate by 12 weeks and 18 weeks.

Components of tumor assessments (target lesion response, non-target lesion response, new lesion [yes/no]) will be listed. In addition, Cancer Antigen-125 (CA-125) in the assessment of ovarian cancer response, or Prostate-specific antigen (PSA) in the assessment of prostate cancer response will also be listed.

PFS, TTP and TTR will be summarized and graphed using the Kaplan-Meier product-limit method for each patient group. The estimates of the 25th, median, 75th percentiles of the PFS and their 95% confidence intervals will be provided, if applicable. Analyses will be based on

all tumor types combined. For tumor types, separate summaries will be performed by the tumor type.

DOR will be summarized using the Kaplan-Meier method and the median response presented along with 95% confidence interval only if there are sufficient numbers of events, otherwise, only listing of DOR will be provided. Analyses will be based all tumor types combined.

Additionally, a swimmer plot depicting time to onset and duration of response per RECIST 1.1 based on local radiology review will be presented.

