2.7.3 Handling of missing values/censoring/discontinuations

Handling of missing tumor assessments in ORR analysis

For the computation of ORR, in case of solid tumor all confirmed responses (CR or PR) reported up to the analysis cut-off will be included. Patients with no valid radiological assessment or unconfirmed responses will be considered as non-responders. In particular, patients with CR or PR at the last radiological assessment prior to cut-off and no response at the previous assessment are by definition unconfirmed and will be considered as non-responders for the primary analysis.

Patients with unknown or missing BOR will be counted as failures (non-responders). If there is no baseline tumor assessment, all post-baseline overall lesion responses are expected to be 'Unknown'. If no valid post-baseline tumor assessments are available, the BOR must be 'Unknown' unless progression is reported. For the computation of ORR, these patients will be included in the FAS and will be counted as 'failures'.

Censoring rules TTP and PFS calculation

If a patient has not progressed or is not known to have died due to underlying cancer or has received any further anti-neoplastic therapy in the absence of progression, at the analysis cutoff date, will be censored at the date of the last adequate tumor assessment before the cut-off date or before the start of the new anti-neoplastic therapy date, whichever is earlier. Patients who do not have any post-baseline tumor assessment will be considered as censored at Day 1.

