2.14 Interim analysis

Scheduled interim data reviews will occur for the primary endpoint of clinical benefit rate only as required by the Bayesian Hierarchical design. The first interim data review will be performed after the 5 subjects have CBR data available within a cohort. Interim analyses will continue every 3 months thereafter provided at least 10 subjects contribute new CBR data to the subsequent interim. At each interim analysis, the tumor cohorts will be evaluated for early futility and early success by comparing posterior quantities for the response rate to pre-specified early stopping criteria.

There is no plan for a formal interim analysis of safety or other secondary endpoints for this study. However, for publication or other purposes, interim data review of clean data will be performed as necessary. At these interim reviews, patient demographics/baseline characteristics, the primary and secondary endpoints as applicable, and all important safety endpoints will be summarized. No formal report will be issued for these data reviews.

3 Sample size calculation

The sample size was chosen by the usual criteria of obtaining adequate power for the alternative hypothesis of interest as given in Sections 6.2.2 and 6.2.3 of Appendix 4 of protocol. This hypothesis corresponds to a generally effective treatment across cohorts and incorporates variation in treatment effects to reflect the realistic expectation that treatment effects may differ by cohort. In this setting, analytical power calculations are not possible, but the design was simulated to obtain the power of the study as shown in the appendix. The sample sizes shown (minimum of 5 for futility stopping, minimum of 10 for early success and maximum of 24 as a cohort cap) achieve adequate power for the alternative hypothesis. The simulations included the expected variable accrual by simulating a Poisson process with expected accrual also shown in the appendix.

4 Change to protocol specified analyses

As per study team suggestion, the definitions of full analysis set (FAS) and safety set have been changed(defined in [section 2.2](#)).

5 Appendix

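### SAP 2.7.1 puts a 24-week limit on the solid-tumour secondary ORR that the protocol does not have and that SAP 2.7.3 contradicts

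*SAP*

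**What the plan says.** **Protocol.** Section 10.5.1 states: "The overall response rate (ORR, PR plus CR) and its 95% exact confidence interval will be provided for each patient group". No time limit is attached there or in Table 3-1. Appendix 1 (14.1.17) bases ORR on best overall response and defines that as follows: "The best overall response is the best response recorded from the start of the treatment until disease progression/recurrence". Treatment may last up to 2 years.

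**SAP 2.7.1.** For solid tumours, "the assessment criteria will be RECIST 1.1 and will include responses of CR and/or PR for ≤ 24 weeks". The sentence on haematological tumours names the response criteria and gives no window. The same bullet closes with: "Additionally, estimates with corresponding 95%CI will also be provided for ORR by end of study".

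**SAP 2.7.2.** After the ORR summaries, "the above analysis will also be repeated for overall response rate by 12 weeks and 18 weeks".

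**SAP 2.7.3.** In the rule for computing ORR, "in case of solid tumor all confirmed responses (CR or PR) reported up to the analysis cut-off will be included".

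**SAP section 4.** The list of departures from the protocol says only that "the definitions of full analysis set (FAS) and safety set have been changed". It does not mention the ORR window.

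**The concern.** Two SAP rules for the same named endpoint give different numerators, and one of them departs from the protocol without being declared. With ORR by 12, 18 and 24 weeks, to cut-off and by end of study all in the plan, nothing says which one is the protocol's secondary ORR. In an open-label study with no ranking of secondary endpoints, the figure quoted as the ORR could then be chosen once results are known.

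The window also fits poorly with what the protocol says about this drug class. Section 2.2 notes that "there are limitations to using time-dependent overall response rate as the primary endpoint", because benefit may show as lasting stable disease or delayed response. Section 7.1.4 says that responses can take weeks or months to appear.

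The reported results may also fail to reconcile. Duration of response (DOR) and time to response (TTR) in SAP 2.7.1 carry no 24-week limit, so their responder counts can exceed the numerator of the ORR defined just above them.

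**Working it through.** The documents give no target, power or interval width for ORR, so there is no plan figure to reproduce. The check compares the texts and then lays out the scan calendar.

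**1. Windows side by side**

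| Place | Window for ORR |
|---|---|
| Protocol 10.5.1 and Table 3-1 | none |
| Protocol Appendix 1, 14.1.17 | treatment start to progression or recurrence |
| SAP Table 1-2 | none |
| SAP 2.7.1, solid tumours | up to 24 weeks |
| SAP 2.7.1, haematological tumours | none stated |
| SAP 2.7.1, additional estimate | end of study |
| SAP 2.7.2, repeats | 12 and 18 weeks |
| SAP 2.7.3, solid tumours | analysis cut-off |

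SAP 2.1 uses data up to the point where all patients have stopped or completed 2 years of therapy and 150 days of safety follow-up. The cut-off in 2.7.3 is therefore far later than week 24.

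**2. Calendar**

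Inputs: scheduled scans at weeks 12, 18 and 24, then every 12 weeks (Protocol 4.1 and 7.2.1.1); solid-tumour CR or PR confirmed at least 4 weeks after first observation (Protocol 10.4, SAP 2.5.2). The earliest scheduled confirming scan for each first observation is:

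- week 12: week 18
- week 18: week 24
- week 24: week 36
- week 36: week 48

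Which scheduled-scan responses count therefore depends on a choice that the SAP does not state:

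| Window | Dated by first observation, confirmed later | Confirmation must also fall inside |
|---|---|---|
| 12 weeks | first seen at 12 | none possible |
| 18 weeks | first seen at 12 or 18 | first seen at 12 |
| 24 weeks | first seen at 12, 18 or 24 | first seen at 12 or 18 |

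A response first seen at week 36 or later is outside every windowed version under either reading. It is inside the end-of-study ORR and the 2.7.3 rule.

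**3. DOR and TTR**

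Take a solid-tumour patient with PR first seen at week 36 and confirmed at week 48. Under SAP 2.7.1 this patient contributes a duration of response and is an event for TTR, but is not a responder in the 24-week ORR.

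**4. Size**

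One late responder shifts a cohort's ORR by 1/n:

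- n = 24 (the cap for the primary population): 1/24 = 4.2 points
- n = 10 (cohort size before expansion, and the smallest solid-tumour cohort that SAP 2.7.2 summarises on its own): 1/10 = 10 points

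For illustration, with assumed responder counts and exact (Clopper-Pearson) 95% intervals:

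| n | Responders by week 24 | ORR (95% CI) | With one late responder added |
|---|---|---|---|
| 24 | 3 | 12.5% (2.7 to 32.4) | 16.7% (4.7 to 37.4) |
| 10 | 2 | 20.0% (2.5 to 55.6) | 30.0% (6.7 to 65.2) |

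**The case against.** The best defence is that nothing is lost. The same bullet plans ORR by end of study with a confidence interval, and 2.7.3 counts responses to the cut-off. No key secondary endpoint exists (SAP 2.6), and SAP 2.1 makes everything except the primary variable descriptive. On the undefined date, the SAP's DOR rule starts a response when it is first seen, and Appendix 1 (14.1.24 and 14.1.25) does the same, so the windows could be read that way.

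Much of this stands, and it rules out several stronger readings that a reader might infer:

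- **That late responders disappear and ORR is biased downward.** They are missing only from the 24-week version. The documents give no share of responses arriving after week 24, so no bias can be quantified. Counting scans after week 24 does not supply one, because scans are not responses and patients who progress early never reach the later scans.
- **That ORR by 12 weeks must be zero.** This follows only if confirmation must fall inside the window and only scheduled scans are used. The SAP does not say the first, and Protocol 4.1 allows extra assessments.
- **That Protocol 2.2 forbids a windowed ORR.** That section explains why clinical benefit rather than ORR is primary and sets no ORR window. Its 30-month median time to response concerns complete responders with melanoma under CTLA-4 blockade, and it exceeds this trial's 2-year treatment maximum.

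What does not stand is the idea that 2.7.3 settles the matter. Almost the same sentence appears in SAP 2.5.3 for the clinical benefit rate, which is itself a 24-week measure. It therefore cannot safely be taken to override the explicit limit in 2.7.1. Nor does an additional estimate remove the contradiction or declare the departure.

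**Conclusion.** The point holds as an inconsistency and an undeclared departure from the protocol. The solid-tumour ORR named in SAP 2.7.1 is not the protocol's ORR and is not what SAP 2.7.3 computes. The limit is written for solid tumours and not for lymphoma, so on the text one label covers two different measures.

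The effect is modest. Each patient whose response falls outside the window changes the named figure by 4.2 points in a cohort of 24 or 10 points in a cohort of 10, which is small beside the exact intervals above. How many such patients there will be cannot be derived from the documents. The calendar result assumes scheduled scans and the 4-week confirmation rule. The primary decision on clinical benefit is not touched.

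**What to change.** - In SAP 2.7.1, define the secondary ORR for every cohort on confirmed best overall response until progression, using assessments up to the analysis cut-off. Confirmation applies where the plan already requires it (solid tumours), and the Appendix 1 rules on scans after treatment ends or after new therapy stay unchanged. This agrees with 2.7.3, Protocol 10.5.1 and Appendix 1, and gives ORR, DOR and TTR the same responders.
- Label the 12-, 18- and 24-week versions supportive. Classify each patient by the date the response was first observed, provided it is later confirmed, and state how the 7-day scan allowance is treated.
- If the 24-week version is kept as the named endpoint, say so in section 4 with a reason, and state whether it applies to lymphoma.

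The cost is SAP wording. The end-of-study estimate is already planned, and no new data are needed. The SAP's document history shows changes made after database lock, so the entry should carry its date.

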7.2.1.1 Radiological Tumor Assessment

At screening, all patients will undergo CT with i.v. contrast of the chest, abdomen and pelvis. Additionally, patients with lymphoma will also undergo CT with i.v. contrast of the neck and a PET scan. MRI should only be used to evaluate sites of disease that are not adequately imaged by CT. If a patient is intolerant of iodine-based contrast agents, CTs may be performed without contrast. MRI may be used to evaluate sites of disease where a CT without i.v. contrast is not adequate. Visible skin lesions and easily palpable subcutaneous tumors may be measured by physical examination using a ruler or calipers. Ultrasound should not be used to measure sites of disease.

No modality change would be allowed during the study when assessing overall tumor status. For subsequent scans in the same patient, the radiologist must account for all lesions that were present at screening and must use the same technique as used at screening. If possible, a single radiologist should perform all tumor response evaluations for an individual patient. Only in exceptional cases when during the study a patient develops intolerance to the CT scan contrast medium, a CT scan without contrast will be acceptable to avoid modality change.

Tumor assessments will be performed at the time points specified in [Table 7-1](#).

Radiological disease assessments will be performed every 6 weeks (± 7 days), starting 12 weeks after first dose of study drug and continuing through week 24. The frequency of radiological disease assessments will be reduced to every 12 weeks after patients have completed 24 weeks on treatment and will continue until confirmed disease progression. Solid tumor response will be determined locally according to RECIST 1.1 (Appendix 1). Lymphoma response will be determined locally according to Revised Response Criteria for Malignant Lymphoma, (Cheson et al 2007) (Appendix 2).

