14.1.21 Time to progression

Some studies might consider only death related to underlying cancer as an event which indicates progression. In this case the variable “Time to progression” might be used. TTP is defined as PFS except for death unrelated to underlying cancer.

Time to progression (TTP) is the time from date of randomization/start of treatment to the date of event defined as the first documented progression or death due to underlying cancer. If a patient has not had an event, time to progression is censored at the date of last adequate tumor assessment.

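### TTP records no event for patients who die or decline from their cancer before a scan, so its Kaplan-Meier curve is biased upward, and the documents disagree on how cancer deaths should count

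*SAP*

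**What the plan says.** **Event.** SAP 2.7.1: "Time to Progression (TTP) defined as the time from the date of first dose to the date of first documented disease progression or relapse". Protocol Table 3-1 and 10.5.1 define TTP the same way, with no death component.

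**Deaths.** SAP 2.7.1 adds: "Died subjects without documented progression will also be censored at the date of last adequate tumor assessment".

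**No scan after baseline.** SAP 2.7.3, under a heading that covers both TTP and PFS: "Patients who do not have any post-baseline tumor assessment will be considered as censored at Day 1". SAP 2.2.1 also takes patients with no post-baseline assessment out of the FAS, which is the efficacy set.

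**First scan.** Protocol 7.2.1.1 schedules imaging every 6 weeks, "starting 12 weeks after first dose of study drug and continuing through week 24".

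**Progression without a scan.** SAP 2.7.1 makes it an event for PFS: "Disease progression noted as the reason for discontinuation of treatment will also be considered as a progression event for PFS analyses". SAP 2.5.2 treats progression as progressive disease for CBR when it is the reason for stopping treatment or the cause of an on-treatment death. Nothing equivalent is stated for TTP.

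**Appendix 1 of the protocol.** Section 14.1.21 makes the TTP event "the date of event defined as the first documented progression or death due to underlying cancer". Table 14-5 situation G and the censoring reasons in 14.1.39 agree: for TTP, only deaths not due to the study cancer are censored. Situation E, on discontinuation for progression without documentation, is ignored by default.

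**The concern.** Kaplan-Meier estimation (SAP 2.7.2) assumes that censored patients have the same outlook as those still at risk. Here a patient is censored because the cancer killed them or made them too ill to scan, so the censoring is informative. If this happens before any post-baseline scan, the patient leaves the risk set at Day 1 or is never in the analysis set. The TTP curve then describes patients well enough to reach a scan, and it sits too high most clearly in the tumors that progress fastest.

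The documents also leave the programmer without one rule. SAP 2.7.1 censors cancer deaths and Appendix 1 counts them. SAP section 4 declares only the changes to the FAS and safety set, so this departure from Appendix 1 is not listed.

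**Working it through.** **1. Reproduce the plan's own figures.** Protocol Appendix 4, section 6.1.2, derives historical CBR from median PFS m (months) under an exponential model: CBR = 0.5^(6/m). For m = 1.5, 5, 6.2, 4, 3, 5, 3 this gives 6.25, 43.53, 51.13, 35.36, 25.00, 43.53 and 25.00%. The stated values are 6.25, 43.50, 51.10, 35.40, 25.00, 43.50 and 25.00%. The model is confirmed and is used below for scale.

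**2. Share of events before the first scheduled scan.** With the SAP 2.1.1.9 month of 30.3475 days, week 12 is 84/30.3475 = 2.768 months. The share is P = 1 - 0.5^(2.768/m). For SCLC, P = 1 - 0.5^(2.768/1.5) = 0.722.

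**3. Effect on the curve.** Let c be the share of those events that are cancer deaths or clinical progressions with no scan. The documents give no value for c; I assume 10% to 50%. Removing a proportion cP at Day 1, or excluding it from the FAS, gives the same curve: the week-12 estimate becomes S12/(1 - cP), where S12 = 1 - P.

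- SCLC, c = 10%: 0.278/(1 - 0.072) = 0.300
- SCLC, c = 25%: 0.278/(1 - 0.180) = 0.340
- SCLC, c = 50%: 0.278/(1 - 0.361) = 0.435

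| Group (median PFS, months) | Event before week 12 | Progression-free at week 12, model | c = 10% | c = 25% | c = 50% |
|---|---|---|---|---|---|
| SCLC (1.5) | 72% | 28% | 30% | 34% | 44% |
| Ovarian, DLBCL (3) | 47% | 53% | 55% | 60% | 69% |
| Prostate (4) | 38% | 62% | 64% | 68% | 76% |
| Gastroesophageal, NET (5) | 32% | 68% | 70% | 74% | 81% |
| STS (6.2) | 27% | 73% | 75% | 79% | 85% |

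The proportion removed, cP, is 7% to 36% in SCLC (0.7 to 3.6 patients in a cohort of 10) and 3% to 13% in STS. Every point from week 12 onward is raised by the factor 1/(1 - cP), which in SCLC is 1.08 to 1.56.

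**4. Medians.** A simulation with true event dates gave TTP medians, for c = 10%, 25% and 50%, of 1.6, 1.7 and 2.2 months in SCLC (true 1.5) and 3.2, 3.5 and 4.2 in ovarian/DLBCL (true 3.0). If progressions are dated at scheduled scans, medians move in steps. SCLC stays at 12 weeks throughout this range; it would pass week 12 only if 0.278/(1 - 0.722c) exceeded 0.5, that is c above about 61%. Ovarian/DLBCL moves from 18 to 24 weeks only at c = 50%, while prostate moves from 18 to 24 weeks already at 10%.

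**The case against.** **The SAP follows the protocol body.** Table 3-1 and 10.5.1 define TTP without deaths, and Appendix 1 is a general guideline that leaves study-specific decisions to the protocol or analysis plan. This stands. A reader might infer that SAP 2.7.1 breaks the protocol's TTP definition; the conflict is with Appendix 1 only.

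**Ignoring undocumented clinical progression is the Appendix 1 default.** This also stands, so that part is an inconsistency with the SAP's own PFS and CBR rules, not a departure from Appendix 1. Section 14.1.27 does allow the event option where early progression is common or deterioration prevents assessment. The default relies on continued follow-up for progression, which a patient who dies early cannot have.

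**SAP 2.7.3 does not clearly side with Appendix 1.** Its words "If a patient has not progressed or is not known to have died due to underlying cancer" could imply that cancer deaths are events. The conditions are joined by "or", however, so not having progressed may be enough for censoring, and the sentence is shared with PFS. It is ambiguous, not contrary.

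**An unscanned early death need not be a PFS event either.** It is tempting to say that such a patient counts in PFS but not in TTP. The Day-1 sentence covers both endpoints, and SAP 2.2.1 may exclude the patient from both. The documents do not settle this.

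**The size is assumed.** Protocol 7.2.1 requires prompt assessment when progression is suspected, and 4.1 requires progression leading to discontinuation to be clearly documented. Both push c down, but neither covers sudden death or decline too rapid to scan.

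**Nothing is decided on TTP.** It is descriptive, and TTP lies above PFS by definition once some deaths are excluded, so a gap between the curves is not in itself evidence of bias.

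**Conclusion.** The point holds as an upward bias in a descriptive secondary endpoint, together with an unreconciled rule for cancer deaths. The direction follows from the text; the size does not. Under the protocol's historical medians and exponential model, with c between 10% and 50%, SCLC progression-free at week 12 reads about 30% to 44% against 28%, and the median may not move if events are dated at scheduled scans.

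Three assumptions matter. The value of c is not in the documents. The medians are for PFS, so P includes some deaths from other causes that TTP may properly censor. Only patients with no post-baseline scan go to Day 1; those with an earlier adequate scan are censored there, which is also informative but removes less.

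A reader might infer that cohort conclusions are at risk. They are not: success rests on CBR, which treats these patients as failures when they are in the analysis set.

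**What to change.** - In SAP 2.7.1, define the TTP event as the first of: documented progression or relapse; discontinuation with disease progression as the reason; death from the study indication. Censor only other deaths, and delete the sentence that censors all deaths without documented progression.
- In SAP 2.7.3, apply the Day-1 rule only to patients with none of these events, and reword the joint TTP/PFS sentence so that each endpoint has its own rule.
- In SAP 2.2.1, keep treated patients without a post-baseline assessment in the FAS. SAP 2.5.3 and 2.7.3 already count patients with no valid post-baseline tumor assessment in the FAS for CBR and ORR.
- In SAP section 4, list the change from protocol Table 3-1 and 10.5.1.
- Report the number censored at Day 1 in each cohort, and give the documented-progression-only version as a sensitivity analysis.

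**Cost.** SAP wording, one derived variable and one extra run. Discontinuation reason and cause of death are already collected. TTP estimates become shorter, and some causes of death may be missing: SAP 2.8.2 lists principal cause only where available. The SAP's change log already includes an entry made after database lock, so a change made now must be labelled as post hoc, which is a further reason to show both versions.
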